APPENDIX 3 - OUTCOME MEASURES SUMMARY AND SCORING TABLE

Definition	Scoring	Item coding	Subscales	Direction	Missing value rules	Thresholds
Standard Clinical Interview for Dependence – Research version SCID-RV						
No reference available; below scoring derived from MACRRO database						
Structured Clinical Interview for DSM-5 (SCID-5) is a semi structured interview guide for making the major diagnoses.	Two single item scales (one for opioid and one for cocaine). Remission status is to be calculated from the SCID. Remission is satisfied (i.e. 'yes') if no symptoms are present that is a score of 1 or lower is obtained. If a score of 2 or more is given then remission status is 'no'.	Items are coded on a 5 point scale based on number of symptoms present; no symptoms, 1 symptom, Mild (2 – 3), Moderate (4-5) and Severe (6 or more)	None found	Lower better	None found	None found
Clinical Global Impression scale (severity and improvement - CGI-S/CGI-I)						
Busner, J. and Targum, S.D., The Clinical Global Impressions Scale: Applying a Research Tool in Clinical Practice (2007). Psychiatry.						
Brief stand-alone assessment of the clinician's view of the patient's global functioning. The scale comprises two companion one-item measures evaluating the severity of psychopathology and change from the initiation of treatment.	Two single item scales (CGI-S and CGI-I). Both items individually scored on a 1 to 7 point scale. Total score is not to be calculated from the two scales. However, the two scale scores will range from 1 to 7.	The CGI severity ranges from 1 'extremely mild' to 7 'extremely severe'	1. Severity item)	(1 Lower better	None found	1 – Extremely mild 2 – Very mild 3 – Mild 4 – Moderately severe 5 – Severe 6 – Very severe 7 – Extremely severe
Addiction Dimensions for Assessment and Personalised Treatment (ADAPT)						
Marsden, J., et al., Development of the Addiction Dimensions for Assessment and Personalised Treatment (ADAPT). Drug Alcohol Depend. (2014), http://dx.doi.org/10.1016/j.drugalcdep.2014.03.018						

Used for substance use disorders (SUD) clinicians to obtain a brief multi dimension patient profile of addiction related severity, health and social problem complexity and recovery strengths	A 14 item measure consisting of three subscales. Each subscale total is calculated by summing the individual items in the subscale. An overall measure total score is not obtainable, just 3 subscale scores.	Items 1, 3, 4, 5, 9, 10 rated; 0 'None' and 1 'Present' Items 2, 5, 6, 7, 8, 11, 12, 13, 14 rated 0 'None', 1 'Low', 2 'Moderate' and 3 'High'.	1. Addiction severity (items 1 – 3). 2. Coexisting problem complexity (items 4 – 10). 3. Recovery Strengths (items 11 – 14)	1. Higher scores indicate worse 2. Higher scores indicate better 3. Higher scores indicate better	None found None found None found	1. Low 0 – 1, moderate 2 – 3 and high 5 – 4 2. Low 0 – 2, moderate 3 – 5 and high 6 – 15 3. Low 0 – 5, moderate 6 – 8 and high 9 – 11
Craving response using Craving experience questionnaire (CEQ-F)						
No reference available; below scoring derived from MACRO database						
Craving Questionnaire						
Craving Experience	11 item scale.	Each item rated on a scale from 0 – 10.	None identified	Higher scores indicate more severe craving	None found	None found
Total scale calculated by summing the 11 items, therefore final score ranges from 0 to 110.						
Visual analogue craving rating (Need/Want) (VAS-N/VAS-W)						
No reference available; below scoring derived from MACRO database						
Self-report craving rating	Two individual items one measures rating need and the other rating want.	Both items are scored on a 0 – 100 continuous scale	None identified	Higher scores indicate more severe craving	None found	None found
Total score is not to be calculated from the two scales. However, the two scale scores will range from 0 to 100.						
Social functioning using Work and Social Adjustment Scale (WSAS)						
Mundt, J C., et al., The Work and Social Adjustment Scale: a simple measure of impairment in functioning (2002). British Journal of Psychiatry , 180, 461 – 464.						

Self-report scale of functional impairment attributable to an identified problem.	Five item scale. Total score calculated by summing up 5 items in the scale.	Items rated on a 0 to 8 scale with 0 indicating no impairment and 8 indicating very severe impairment	None identified	Higher scores indicate better state.	None found	None found
Quick Inventory of Depressive Symptomatology (QIDS-SR) Rush, A. J., Trivedi, M. H., Ibrahim, H. M., Carmody, T. J., Arnow, B., Klein, D. K., ... Keller, M. B. (2003). The 16-item quick inventory of depressive symptomatology (QIDS), clinician rating (QIDS-C), and self-report (QIDS-SR): a psychometric evaluation in patients with chronic major depression. Biological Psychiatry , 54, 573-583. http://www.ids-qids.org/Scoring_Instructions.pdf http://www.ids-qids.org/index2.html#table2						
self-report measure of depression	16 item scale. Subscales calculated by taking highest score of any one item of the subscale. Total score for each subscale ranging from 0 to 3 Total score calculated by summing the 9 subscales therefore total scores range from 0 to 27.	Items rated on a 0 to 3 scale; 0 indicating no symptom and 3 indicating worse.	1. Sleep disturbance (items 1 - 4) 2. Sad mood (item 5) 3. Decrease/increase in appetite or weight (items 6 - 9) 4. Concentration (item 10) 5. Self-criticism (item 11) 6. Suicidal ideation (item 12) 7. Interest (item 13) 8. Energy/fatigue (item 14) 9. Psychomotor agitation/retardation (items 15 - 16)	Higher scores worse for all subscales	None found	For total score 1-5 = No depression 6-10 = Mild depression 11-15 = Moderate depression 16-20 = Severe depression 21-27 = Very severe depression
Self-report measure to assess person at recovery from drug and/or alcohol dependence	21 item scale. Items 1 – 3 scored;	Section A (items 1 – 3) rated on a 5 point scale 1 – 5; ranging from 1 'Never' to 5 'everyday'	1. Drinking and drug use (items 1 – 6) 2. Self-care (items 7 – 11)	Individual items indicates lower better and higher worse but scores are then weighted higher if lower so	None Found	None Found

Improvement and Recovery using Substance Use Recovery Elevator (SURE)

Self-report measure to assess person at recovery from drug and/or alcohol dependence

Section A (items 1 – 3) rated on a 5 point scale 1 – 5; ranging from 1 'Never' to 5 'everyday'	1. Drinking and drug use (items 1 – 6) 2. Self-care (items 7 – 11)	Individual items indicates lower better and higher worse but scores are then weighted higher if lower so	None Found	None Found
--	---	--	------------	------------

'Never' OR 'On 1 or 2 days' = 3, 'On 3 or 4 days' = 2, 'On 5 or 6 days' OR 'Every day' = 1
 
Items 4 – 21 scored; 'All of the time' OR 'Most of the time' = 3, 'A fair amount of the time' = 2, 'A little of the time' OR 'None of the time' = 1
	
Section B (items 7 – 21) rated on a 5-point scale 1 – 5; ranging from 1 'none of the time' to 5 'all of the time'.
 
Section C items not used for measure scoring.
 
Score range for each subscale
 
 1. Drinking and drug use; 6 – 18 2. Self care; 5 – 15 3. Relationships; 4 – 12 4. Material resources; 3 – 9 5. Outlook on life; items 3 – 9 
Total score ranges from 21 – 63
	
3. Relationships (items 12–15)
 
4. Material resources (items 16 – 18)
 
5. Outlook on life (items 19 – 21)
	
total score format is higher scores indicate better.

Patient Reported Outcome Status (severity and improvement - PRO-S/PRO-I)
 
No reference available; below scoring derived from MACRO database
	
Patient reported outcome of severity and improvement of addition problem
	
Two single item scales (PRO-S and PRO-I). Both items individually scored on a 1 to 7 point scale.
 
Total score is not to be calculated from the two scales. However, the two scale scores will range from 1 to 7.
	
The PRO severity ranges from 1 'extremely mild' to 7 'extremely severe'
 
The PRO improvement ranges from 1 'very much improved' to 7 'very much worse'

			
1 – Extremely mild 2 – Very mild 3 – mild 4 – moderate 5 – severe 6 – very severe 7 – extremely severe
 
1 – very much improved 2 – much improved 3 – minimally improved 4 – no change 5 – minimally worse 6 – much worse 7 – very much worse

Emotion regulation using the Difficulties in Emotion Regulation Scale- short form (Emotion regulation using the Difficulties in Emotion Regulation Scale- short form (DERS-SF))


Kaufman, E. A., Xia, M., Fosco, G., Skidmore, C. R., & Crowell, S. E. (2015). The difficulties in emotion regulation scale short form (DERS-SF): Validation and replication in adolescent and adult samples. Journal of Psychopathology and Behavioral Assessment, doi:10.1007/s10862-015-9539-3
	
self-report measure for assessing emotion regulation problems
 
18 item scale
 
Items in each scale summed to give individual scale scores (ranging from 1 to 5) and total score calculated by summing scales, total score ranging from 18 to 90
	
Each item scored on a 5 point scale ranging from 1 'Almost Never' to 5 'Almost always'
 
Awareness scale should be reverse coded so that items range from 1 'almost always' to 5 'almost never'.
 
1. Strategies (items 10, 15 and 18) 2. Non-acceptance (items 7, 12 and 16) 3. Impulse (items 9, 14 and 17) 4. Goals (items 8, 11 and 13) 5. Awareness (items 1, 4 and 6) 6. Clarity (items 2, 3 and 5)
	
Lower scores indicate better
 
None found
 
None found
 
None found
 
None found
 
None found

		
Alcohol quantity, frequency, maximum consumption (ALC-QF (TOP))
 
No reference available; below scoring derived from MACRO database
 
Alcohol – typical Quantity and Frequency. Using an adapted version of the Treatment Outcomes Profile (TOP). The TOP is the standard national instrument for monitoring the outcomes of public substance use disorder treatment services in England.
 
3 items in measure; number of days, average units and maximum units on any given day.
 
Maximum units will be reported descriptively. Quantity and Frequency will be treated as two separate items.
 
Items rated based on number of drinking days in past four weeks; 0 to 28
 
Units given on scale from 0 to 100
 
Maximum units ranges from 0 to 500.
	
None found
 
None found
 
Higher numbers indicate more drinking days and units.
 
None found
 
None found
 
None found

The Montreal Cognitive Assessment (MoCA)

Original ref: Nasreddine Z.S., Phillips N.A., Bédirian V., Charbonneau S., Whitehead V., Collin I., Cummings J.L., Chertkow H. The Montreal Cognitive Assessment (MoCA): A Brief Screening Tool for Mild Cognitive Impairment. *Journal of the American Geriatrics Society*, 53 (2005) 695-699.


Evaluates whether someone's thinking ability is impaired
 
10 item scale, with an additional item (No. 11) to indicate education level.
 
Items 1-10 are summed together to give a total score ranging from 0 to 30.
	
10 items are rated on various scales (0 to 1, 2, 3, 5 and 6)
	
Higher numbers indicate less cognitive impairment
	
If education level is missing then items 1-10 should still be calculated.
	
Item 11 A score of 26 or above is considered normal.

---	---	--	--	---

	
An extra point is awarded if item 11 is 'Yes' (i.e. subject has 12 years or fewer of formal education),
 
However, the max score is 30 so if a participant scores 30 out of 30 this additional point isn't added.
	

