9.1 By visit

The following standardised instruments will be administered during the study:

Urine drug screen (UDS; detection sensitivity: opiates: 2000ng/ml; cocaine and benzodiazepines: 300 ng/ml; window of detection: 72 hours; UDS procedure conducted each visit). A tamper-proof, instant result, immunoassay device (e.g. E-Z Split Key Cup; www.concateno.com) will screen for recent use of opioids, cocaine and benzodiazepines. The device uses a control line and a temperature sensor (required range: 92°-96 °F) to indicate that a valid test has been done. The UDS product for the study also includes measurement of Bup and Met (providing a proxy indicator of medication adherence) and also (meth)amphetamine and cannabis (for description and exploratory analysis).

* **Structured clinical interview for DSM-5 disorders – research version** (SCID-5-RV [34]). The SCID-5-RV contains a checklist of 11 symptoms (presence or absence) to diagnose the severity of current OUD (mild: 2–3 symptoms; moderate: 4–5; severe: ≥ 6). The American Psychiatric Association's definition for early OUD remission will be applied at 3-month follow-up (i.e. without substance use disorder criteria [except] craving, using the “on maintenance therapy” specifier as appropriate).

Alcohol - Quantity, Frequency and Maximum Consumption (ALC-QFM) This information will be recorded using an adapted version of the **Treatment Outcomes Profile** (TOP [54]). The TOP is the standard national instrument for monitoring the outcomes of public substance use disorder treatment services in England.

Time-Line Follow-Back (TLFB) interview for heroin, cocaine and benzodiazepine recorded for each day whether the participant reports using or not using these drugs. The TLFB, calendar-prompt interview will be adapted from the TOP.

Montreal Cognitive Assessment (MoCA; [35]. The MoCA is a brief screening instrument for mild cognitive impairment and assesses attention, concentration, working memory, visuo-constructional skills, and conceptual thinking. A score of ≥ 26 is considered to reflect normal range functioning. An alternate version of the MoCA will be used at follow-up to decrease the risk of learning effects. The MoCa will be completed on 2 visits: baseline (version 7.1) and study week 12 (version 7.2).

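### SAP Appendix 3's remission score does not reproduce the protocol's OUD remission rule at week 12 under any coding, so some one-symptom participants would be misclassified

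*SAP*

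**What the plan says.** **Protocol 9.1 (SCID-5-RV).** "The SCID-5-RV contains a checklist of 11 symptoms (presence or absence) to diagnose the severity of current OUD". The American Psychiatric Association's "definition for early OUD remission will be applied at 3-month follow-up", and remission means being "without substance use disorder criteria [except] craving". The same sentence adds the specifier for patients on maintenance therapy, as appropriate.

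**SAP Appendix 3 (SCID-RV).** The measure is described as follows: "Two single item scales (one for opioid and one for cocaine". For coding, "Items are coded on a 5 point scale based on number of symptoms present; no symptoms, 1 symptom, Mild (2 – 3), Moderate (4-5) and Severe" (the last category being 6 or more). The rule for a yes is "Remission is satisfied (i.e. 'yes') if no symptoms are present that is a score of 1 or lower is obtained". The rule for a no is "If a score of 2 or more is given then remission status is 'no". The appendix says that no reference is available and that the scoring was taken from the trial database. It does not give the numbers attached to the five categories, and it mentions neither craving nor the maintenance-therapy specifier.

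**Use of the rule.** SAP Appendix 2 sends the binary logistic regression of remission at 12 and 24 weeks directly to the Appendix 3 scoring. SAP 5.2 (Objective 4) and Protocol 10.2 list OUD and CUD remission as a secondary outcome. Neither gives a separate definition for CUD.

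**The concern.** The protocol permits one named symptom to persist in remission. The SAP works from how many symptoms there are, without regard to which. The two rules can therefore disagree about a participant with one symptom.

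The SAP's yes rule also ties an absence of symptoms to a score of 1 or lower. That is consistent only if the lowest category is coded 1. If it is coded 0, a score of 1 means one symptom, and the sentence contradicts itself.

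At stake is the reported remission rate for a named secondary objective. Two programmers could follow the SAP faithfully and obtain different rates from the same records. Neither would be applying the protocol's definition.

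**Working it through.** The documents give no figure to reproduce, because this is a classification rule. The check classifies every possible symptom pattern under both rules.

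**Inputs**
- 11 criteria, each present or absent, one of which is craving (Protocol 9.1): 2^11 = 2,048 patterns.
- Protocol rule: yes if no criterion other than craving is present.
- SAP rule: yes if the score is 1 or lower, with categories "no symptoms, 1 symptom, Mild (2 – 3), Moderate (4-5) and Severe (6 or more"). The codes are unstated, so 0-4, 1-5 and a raw count of 0-11 are each tried.

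**Patterns by number of symptoms:** none, 1; exactly one, 11 (1 craving only, 10 another symptom only); two or more, 2,048 - 12 = 2,036.

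**Classification**

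| Pattern | Number | Protocol | SAP, codes 0-4 or raw count | SAP, codes 1-5 |
|---|---|---|---|---|
| No symptoms | 1 | yes | yes | yes |
| Craving only | 1 | yes | yes | **no** |
| One symptom, not craving | 10 | no | **yes** | no |
| Two or more | 2,036 | no | no | no |

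- Codes 0-4 or raw count: the SAP says yes to 1 + 11 = 12 patterns and the protocol to 2. They disagree on 12 - 2 = 10, all with a single non-craving symptom.
- Codes 1-5: the SAP says yes to 1 pattern and the protocol to 2. They disagree on 2 - 1 = 1, craving only.
- With no symptoms, or with two or more, the rules agree under every coding.

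**Why no recoding helps.** All 11 one-symptom patterns share one category. The protocol puts 1 of them in remission and 10 out. A cut-off on the category must treat all 11 alike.

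**Scale.** The figures above count patterns and say nothing about how many patients show each one. The documents do not say how common one-symptom records are. As an illustration, take 152 per arm (Protocol 5.2) and the plan's 15% attrition allowance as a loss: 152 x 0.85 = 129.2, about 129 per arm. If 5% had one symptom, 0.05 x 129 = 6.5; if 20%, 0.20 x 129 = 25.8. That gives about 6-26 per arm. This is a ceiling, because each coding misclassifies only part of the one-symptom group.

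**The case against.** **Scope.** The protocol words its definition for OUD at 3 months. It gives no rule for CUD or for week 24. This stands. The conflict between documents is established for OUD at week 12. Extending it further is an inference, reasonable because no other remission definition is given. Read strictly, for CUD and week 24 the only contradiction is the SAP's own, and only if the lowest category is coded 0.

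**The milder coding may be the real one.** Other five-point items in Appendix 3 (SURE, DERS-SF) run from 1 to 5. On that coding the SAP agrees with itself and only craving-only cases differ. Against this, the words 'or lower' have no purpose if no code lies below 1. The documents do not settle the coding, and a conflict with the protocol remains either way.

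**Below the mild threshold.** Having 0-1 symptoms falls short of mild disorder (2-3), so a cut-off at one symptom is coherent in itself. It is still a different definition from the protocol's, and it does not fit the SAP's own reference to an absence of symptoms.

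**Stronger readings.** A reader might infer that everyone with exactly one symptom is misclassified. No coding does that. A reader might also infer that, because the injection acts on craving, the one-symptom group is where the arms will differ most. The documents do not show this. Protocol 4.2 reports attenuated craving against placebo and says there has been no head-to-head comparison with standard oral medication. Craving-only cases are, in any event, misclassified only under codes 1-5.

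**Importance.** SAP 4.3 treats all secondary outcomes as exploratory. That limits the consequence, but a stated rule should still give the intended classification.

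**Conclusion.** The point holds in a limited form. As written, the Appendix 3 score does not deliver the protocol's remission definition for OUD at week 12 under any coding, and nothing elsewhere in the SAP repairs it. The error is confined to participants with exactly one symptom and affects only some of them. Codes 0-4 or a raw count overstate remission by including single non-craving cases. Codes 1-5 understate it by excluding craving-only cases. The number affected is unknown, and the 6-26 per arm rests on an assumed prevalence. For CUD and week 24 the defect is a missing definition more than a demonstrated conflict. The sample size and the primary analysis are unaffected.

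**What to change.** Before database lock, amend SAP Appendix 3 as follows:

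1. State the numeric code of each of the five categories.
2. Reconcile the reference to an absence of symptoms with the cut-off of 1 or lower.
3. Derive OUD remission at week 12 from the individual SCID criteria, as no criterion present other than craving. Say how the maintenance-therapy specifier is applied, since both arms receive maintenance medication.
4. If only the category was entered in the database, check source for records in the one-symptom category to identify the symptom.
5. State explicitly which rule applies to CUD and which to week 24.

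The cost is a wording change and a source check limited to one-symptom records. No new participant data are needed if the checklist was kept in source; the documents do not say whether it was entered item by item. Settling the rule before lock also avoids choosing it with results in view.

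### The ADAPT scoring row in SAP Appendix 3 contradicts itself: problem complexity is labelled in the wrong direction, item 5 is coded two ways, and the top strengths band stops one point below the maximum

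*SAP*

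**What the plan says.** SAP section 5.2 (Objective 5) names ADAPT as the second of two clinician-rated measures at 24 weeks, after the CGI. Appendix 2 makes it a continuous outcome analysed with a GLM and refers to Appendix 3 for scoring.

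The ADAPT row of Appendix 3 describes a 14-item measure with three subscales and no overall total. Its rules are:

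- Scoring: "Each subscale total is calculated by summing the individual items in the subscale".
- Subscales: "1. Addiction severity (items 1 – 3). 2. Coexisting problem complexity (items 4 – 10). 3. Recovery Strengths (items 11 – 14".
- Binary items: "Items 1, 3, 4, 5, 9, 10 rated; 0 'None' and 1 'Present".
- Four-level items: "Items 2, 5, 6, 7, 8, 11, 12, 13, 14 rated 0 'None', 1 'Low', 2 'Moderate' and 3 'High".
- Direction: "1. Higher scores indicate worse 2. Higher scores indicate better 3. Higher scores indicate better".
- Complexity bands: "2. Low 0 – 2, moderate 3 – 5 and high 6 – 15".
- Strengths bands: "3. Low 0 – 5, moderate 6 – 8 and high 9 – 11".

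The row states no reverse coding. The same appendix does state one where it is meant, for the Awareness scale of the DERS-SF. Protocol section 9.1 describes the second ADAPT subscale as covering health and social problems that accompany the addiction.

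**The concern.** Appendix 3 is the only place in the two documents that says how ADAPT items become scores and which way each score points. Three of its entries cannot all be followed.

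1. **Direction.** A sum of problem ratings rises as problems increase, but the table calls a higher sum better. If the results text takes its direction from the table, a treatment that reduced coexisting problems would be reported as having made them worse, and the reverse.
2. **Item 5.** It has two codings with different maximum contributions (1 or 3). The choice affects the week-24 complexity score and also the baseline score, which SAP section 6.7 puts in the model as a covariate. All ADAPT subscales are candidate predictors of missingness (section 4.6). Any that are selected would enter the imputation models and a sensitivity version of the primary model (section 6.9).
3. **Strengths bands.** The best possible total under the listed coding belongs to no band.

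**Working it through.** All inputs come from the ADAPT row of SAP Appendix 3: the two item-coding lists, the subscale composition, the summing rule, the direction entries and the band limits.

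**Step 1: count the item entries.** The binary list has 6 entries and the four-level list has 9, so 6 + 9 = 15 entries for a 14-item measure. Together the lists cover items 1 to 14, and item 5 is the only repeat.

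**Step 2: subscale maxima.** Maximum = (number of binary items × 1) + (number of four-level items × 3).

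| Subscale | Items | Reading of item 5 | Maximum | Top of stated bands |
|---|---|---|---|---|
| Severity | 1–3 | not involved | 2×1 + 1×3 = 5 | 5 |
| Complexity | 4–10 | 0–3 | 3×1 + 4×3 = 15 | 15 |
| Complexity | 4–10 | 0/1 | 4×1 + 3×3 = 13 | 15 |
| Strengths | 11–14 | not involved | 0×1 + 4×3 = 12 | 11 |

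The severity figure is reproduced (its top band is printed with the limits in reverse order, 5 then 4, which is harmless). The complexity figure is reproduced only with item 5 at 0–3. The strengths figure is not reproduced.

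**Step 3: can the listed codings give 11 for strengths?** If k of the four items were binary, the maximum would be 3(4 − k) + k = 12 − 2k, that is 12, 10, 8, 6 or 4 for k = 0 to 4. None of these is 11, so either the band limit or the coding of at least one strengths item is wrong. The documents do not show which.

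**Step 4: size of the item 5 effect.** Suppose the item is recorded 0–3 but scored as absent/present. A rating of 1 is unchanged, a rating of 2 loses 1 point, and a rating of 3 loses 2 points. The complexity score is then too low by 0 to 2. A total of 6 with item 5 rated 2, or of 7 with item 5 rated 3, would become 5 and move from the high band to the moderate band.

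**Step 5: direction.** The complexity items run upward from None to Present or to High, the subscale is their plain sum, and the bands call 6 and above high. Each of these says that a larger number means more problems. Severity is built the same way and is labelled worse when higher; complexity is labelled better. Let β be the adjusted mean difference in complexity, BUP-XR minus comparator. A negative β means a lower burden of coexisting problems on BUP-XR, but the label would have it described as unfavourable. The value of β and its interval do not depend on the label.

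**Step 6: what each entry affects.**

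- Direction label: interpretation of the complexity result only.
- Item 5: the complexity score at baseline and week 24, and the completer versus non-completer comparison for that subscale, but only if 0/1 is programmed.
- Strengths band: nothing in the GLM. ADAPT bands are not used in the models (section 6.7) or the subgroups (section 6.8).

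**The case against.** The strongest reply is that these are transcription slips in a table for an exploratory outcome, and that the rest of the plan protects against most of them. The subscale's name and the protocol's description make the direction label visibly wrong, so an attentive analyst would not follow it. The stated maximum of 15 points to 0–3 for item 5, and with that reading the lists cover each of the 14 items exactly once. The response options are also built into the eCRF. The bands play no part in the planned model. Section 4.3 treats all secondary outcomes as exploratory, and ADAPT is only one of two clinician-rated measures.

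Most of this stands, and it limits what can be claimed. A reader might infer four stronger things that the documents do not support:

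- *That ADAPT scores will be wrong.* Only the item 5 entry can change a score, and only if it is programmed against the table's own range.
- *That the sign of the complexity effect is reversed.* The sum and the GLM estimate are unaffected; the risk is in the interpretation.
- *That the weight of item 5 cannot be determined.* The 0–15 range largely settles it as 0–3, subject to the eCRF.
- *That the top strengths band should simply be extended to 12.* That assumes the item coding is right and the band wrong. A strengths item with some other range could give 11, and the instrument's scoring paper was not available for this review.

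The reply does not remove the direction problem. The label is an explicit scoring statement for a named secondary outcome, no reverse coding supports it, and an analyst who follows the SAP literally would report the complexity result backwards.

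**Conclusion.** The ADAPT row is wrong as written and should be corrected; the consequences are limited.

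- **Main point.** The complexity direction label contradicts the scoring rule. Following it would reverse the interpretation, though not the estimate, of the week-24 treatment effect on one subscale of an exploratory secondary outcome.
- **Second point.** Item 5 is probably a duplicate entry and should be 0–3. If 0/1 were programmed, complexity scores could be up to 2 points too low.
- **Minor point.** A strengths score of 12 has no band. This matters only if bands are reported.

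The definition of the primary outcome is unaffected. The conclusions rest on the SAP's own coding lists and band limits and on the absence of any stated reverse coding for ADAPT. The correct coding of item 5 and the correct strengths maximum are inferred from those figures and need confirmation from the eCRF and the instrument's published scoring.

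**What to change.** Before database lock, amend the ADAPT row of SAP Appendix 3:

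1. State that a higher problem complexity score is worse. If a reverse coding is intended instead, state it explicitly, as is done for the DERS-SF.
2. List item 5 once, with the coding confirmed against the eCRF and consistent with the 0–15 range.
3. Reconcile the coding of items 11 to 14 with the top strengths band, using the eCRF and the instrument's published scoring, and correct whichever is wrong. Put the limits of the top severity band in ascending order at the same time.
4. Check the scoring syntax against the corrected row, including the subscale maxima.

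The cost is a few table edits and one syntax check. No new data are needed and the analysis model does not change. The SAP's change history already records scoring corrections for CEQ-F, WSAS and SURE, so a revision of this kind has precedent.
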